- All findings should be documented: joint swelling, hepatomegaly and splenomegaly, presence of skin rash, ophthalmic control (presence of uveitis). Ophthalmic examination will be performed to examine the presence/absence of uveitis and, if present, the evolution during the study
- Symptoms should be documented: abdominal pain, diarrhea, nausea, vomiting
- All clinical components (including clinical findings and symptoms) of the disease will be captured in a binary way as either being present or absent. The judgement, of whether an end organ category is affected, is done by the treating physician according to clinical standards, as also previously done for all mAIDAI components.
- Daily weight, stool output, and PO intake measurements including number of emesis episodes will be performed on patients with intestinal dysfunction, only when the patients are hospitalized
- Radiologic findings if assessed as necessary by the treating physician

Maintenance co-treatment:

- Total weekly glucocorticoids
- IL-1 blockers
- Other treatments* (e.g., DMARDs, etc.)

*Refer to [Section 11.2.4: Concomitant treatment](#)

Laboratory (see Table 2):

- Serum CRP
- Serum Ferritin
- Complete blood counts
- Serum levels of total IL-18, free IL-18, IL-18BP

Note 1: Gastrointestinal (GI)-related parameters will be assessed in patients with GI dysfunction

Note 2: For outpatient therapy the clinical evaluation will be performed at the monthly visits

DEFINITION OF ACTIVE DISEASE UPON ENROLMENT

- Increased inflammatory markers, i.e. serum ferritin levels ≥ 500 ng/mL or serum CRP $\geq 2x$ ULN, and
- Active clinical disease as evidenced by mAIDAI ≥ 4 or CNS manifestations (i.e. seizures, altered mental status, signs of increased intracranial pressure, chronic papilledema, loss of vision, other sensorineural deficiencies, etc.)

For the definition of active disease upon enrolment, all mAIDAI components (subjective and objective) will be evaluated in line with previous protocol versions.

DEFINITION OF RESPONSE TO THERAPY

1. In the 16-week RW phase, response to therapy (as primary endpoint of efficacy) will be assessed by prevention of disease reactivations during the 16-week treatment in the RW phase
2. In the SAOL phase, response to therapy (as secondary endpoint of efficacy) will be assessed through the control of the active disease

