Severe, systemic inflammatory diseases modulated by IL-18, including MAS and MAS-like disorders, lead to the excessive activation and proliferation of T-lymphocytes and macrophages and lead to hemophagocytosis and overproduction of cytokines. The disease manifestations are: high fever, pancytopenia, hepatitis, hyperferritinemia, and neurologic symptoms (Ravelli, 2002). If left untreated the clinical conditions can progress to coagulopathy, organ failure, and death. These can appear during the evolution of a rheumatic condition, such as SJIA and ASD, triggered by infections or malignancies, or as a result of certain genetic mutations. For example, the protein NLRC4 is a NOD-like receptor whose stimulation recruits and proteolytically activates caspase-1 (Canna et al., 2014) (Romberg et al., 2014). Active caspase-1 cleaves the precursors of IL-1 β and IL-18 to their active forms and induces pyroptotic cell death. Two mutations have been identified in the gene coding for NLRC4, which result in increased NLRC4 inflammasome spontaneous activity and NLRC4-mediated severe systemic inflammation with cases evolving into NLRC4-mediated MAS. In two recent case studies, such mutations resulted in early-onset enterocolitis and recurrent episodes of fever and splenomegaly distinctive for MAS, over time resulting in stunted growth (Canna et al., 2014), (Romberg et al., 2014). Similarly, mutations resulting in deficiency of the XIAP protein are linked with a high susceptibility to develop recurrent HLH, a MAS-like condition involving systemic dysregulation of the immune response in the form of macrophage activation and hemophagocytosis as well as enterocolitis. Patients with XIAP deficiency also show very high IL-18 levels during HLH episodes (Wada et al., 2014).

Tadekinig alfa is a recombinant form of human, soluble IL-18BP isoform a (r-hIL-18BP) that binds to and neutralizes IL-18 with high affinity. The average molecular weight of the full-length polypeptide moiety, calculated per the [redacted] amino acid composition, is approximately [redacted] kDa. The relative molecular mass of the glycosylated molecule is estimated to be approximately [redacted] kDa. The primary structure and N-glycan forms of Tadekinig alfa have been shown to be comparable to the natural protein purified from urine.

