16.8 Withdrawals, Drop-outs, Missing Values

The analysis of the primary endpoint, time to first disease reactivation (including full and partial disease reactivation), will be based on KM survival analysis techniques, where patients who do not experience a disease reactivation during the RW phase will be censored at date of their last assessment for disease symptoms.

Details to account for missing data in the analysis of secondary efficacy endpoints will be described in the statistical analysis plan.

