During the RW-phase, the reference for a disease reactivation (for the primary endpoint assessment) will be the end of the SAOL phase (V8); for the SAOL phase, reference will be the previous visit, as patients enter the SAOL phase with an active disease.

○ **Partial disease reactivation**

- Increase in the number of affected objective end organ damage categories by at least 2 or
- Increase in the number of affected objective end organ damage categories by at least 1 and worsening of at least 1 systemic inflammatory marker (i.e., serum ferritin levels ≥ 500 ng/mL or serum CRP ≥ 2 x ULN) that was meeting complete response criteria before

○ **Full disease reactivation**

- Increase in the number of affected objective end organ damage categories to at least the number of affected end organ damage categories at baseline (V1) and
- Exacerbation of at least 1 systemic inflammatory marker (i.e., serum ferritin levels ≥ 500 ng/mL or serum CRP ≥ 2 x ULN) that was meeting complete response criteria before

Note: It is recommended that patients suffering from *severe* CNS manifestations are put on rescue immunosuppression treatment.

Time to first occurrence of disease reactivation will be calculated in weeks as the date of disease reactivation during the RW phase minus the date of randomization during the RW phase plus 1, divided by 7. Patients who do not experience a disease reactivation during the RW phase will be censored at the date of their last clinical assessment during the RW phase indicating no disease reactivation. Patients will be assessed for disease reactivation during the RW phase at all scheduled or unscheduled visits.

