For all patients enrolled prior to protocol v5.0, the organomegaly subtypes were not explicitly documented with the mAIDAI. Thus, for each visit where organomegaly is indicated as present but no eCRF page of “subtypes of organomegaly” is completed, the subtypes will be evaluated by corresponding entries in the disease history, physical examination, or adverse events. However, as the physical examination after the baseline visit only captures new or worsened conditions, an improvement of one or multiple organomegaly subtypes may not be documented. Thus, all organomegaly subtypes will be documented as ongoing as long as organomegaly is indicated as being present.

7.4.5.3 *Interim Analyses and Data Monitoring*

There are no interim analyses planned for this study. A Data Safety Monitoring Board (DSMB) will convene regularly through the duration of the trial to assess the global safety of TA and advise whether to continue or discontinue the study. Complete details of the DSMB roles and responsibilities are outlined in a separate DSMB charter.

7.4.5.4 *Multicenter Studies*

This is a multicenter study, with approximately eleven clinical sites in the United States, Canada, and Germany. Efficacy data collected from all study centers will be pooled for data analysis. The effect of study center on the efficacy analysis results may be explored post-hoc, as needed.

7.4.5.5 *Multiple Comparisons/Multiplicity*

The overall 2-sided level of significance will be alpha = 0.05 for all statistical testing to include the primary endpoint analysis. The hypothesis testing of selected secondary endpoints collected during the RW phase will be conducted using a gatekeeping procedure based on a closed fixed-sequence test, provided the primary endpoint comparison is statistically significant ($p < 0.05$). This procedure controls the study-wise type I error as described below. In order to evaluate the comparison for each step, all preceding comparisons must have been statistically significant based on a 2-sided alpha = 0.05 in favor of TA.

1. Placebo and TA will be compared with respect to the primary efficacy endpoint, time to first occurrence of disease reactivation experienced during the RW phase
2. Placebo and TA will be compared for the proportion of treatment failures (ie, experience at least one disease reactivation) during the RW phase
3. Placebo and TA will be compared for results of the change from RW Baseline to Week 34/ET in the mAIDAI total score

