7.6 Determination of Sample Size

The primary endpoint of the study is time to first occurrence of disease reactivation (including full and partial disease reactivation) during the RW phase of the study. There is limited historical data for this disease condition, for either a control or an experimental test product, however the frequent recurrence of disease reactivations was expected in the control arm ([Wada 2014](#)). Originally, an 8-week event rate is assumed to be 90% in the placebo group and a considerable reduction in disease reactivations for patients receiving TA was expected. However, a lower event rate was observed from the currently enrolled (still blinded) patients. Thus, the RW phase is prolonged to a maximum of 16 weeks to better assess the effect of TA withdrawal. The power calculations below will assume the same 90% event rate in the SOC arm at 16 weeks. [Figure 1](#) below displays the power achieved for a two-arm study and assumes the following:

- Two-sided log-rank test, with input based on the proportion of patients surviving (ie, event-free) at 16 weeks
- Two-sided alpha = 0.05
- A 1:1 randomization of 10 patients (ie, 5 patients per arm)
- The proportion of patients surviving (ie, event-free) in the control arm at Week 16 of the RW phase is 0.1, which equates to a 90% event rate
- No patients in either group drop out of the study prior to experiencing a disease reactivation or completing the 16 week treatment period as planned
- Total study time is 32 weeks, including a 16-week accrual period and a 16 week follow-up time
- Varying levels of a hazard ratio, from 0.1 to 0.25 in 0.05 increments

Figure 1 Power vs. Hazard Ratio

A hazard ratio of 0.1 equates to an assumed 16-week event rate in the TA group of 20.6% (ie, a survival event-free rate of 79.4%). These assumptions achieve 78.4% power based on a two-sided log rank test with an overall sample size of 10 patients to be randomized in the RW phase (5 in the placebo group and 5 in the TA group). A hazard ratio of 0.1 results in an assumed number of total events among 10 patients to be 6.7, with 4.9 occurring in the placebo group and 1.8 occurring in the TA group.

No power calculations were performed for the SAOL phase of the study, as analysis will be descriptive in nature.

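### A death in the RW phase without a scored reactivation is censored as a non-event, and the treatment-failure rules disagree on the same patient

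*SAP*

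**What the plan says.** The primary event is a partial or full disease reactivation. SAP 6.4.1.1 and Protocol 12.2 define it only by the number of affected objective organ categories, with or without a ferritin or CRP criterion. For everyone else, SAP 6.4.1.1 states: "Patients who do not experience a disease reactivation during the RW phase will be censored at the date of their last clinical assessment"; the sentence goes on to specify an RW assessment that shows no reactivation. Protocol 16.8 has the same rule: "patients who do not experience a disease reactivation during the RW phase will be censored at date of their last assessment for disease symptoms". SAP 7.4.5.2 repeats it.

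The primary estimand (SAP 7.4.2.1) names three intercurrent events: the end of the RW phase, rescue immunosuppression without objective reactivation, and inflammation judged to be infection. Death is not among them. The sensitivity analyses (SAP 7.4.2.3) are a per-protocol repeat and imputations for patients on the 8-week RW design. Deaths appear in a safety listing with their primary cause (SAP 7.5.3).

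Step 2 of the fixed sequence (SAP 7.4.5.5) compares treatment failures. SAP 6.4.1.2 and 7.4.4.2 define failure by reactivation, whereas 7.4.5.2 makes patients with missing data for the evaluation failures.

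On the disease itself, Protocol 8.1 says: "If left untreated the clinical conditions can progress to coagulopathy, organ failure, and death".

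**The concern.** Kaplan-Meier and log-rank methods assume that censored patients have the same outlook as those still at risk. A patient who dies of the disease after withdrawal from active drug does not. Under the written rule the worst possible outcome contributes nothing to the event count.

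In the TA arm this removes a failure of the drug. In the placebo arm it removes a failure of withdrawal, which works against the drug. The two treatment-failure rules then leave open whether the same patient counts in step 2. That would have to be settled after a death is known, and in a trial of about ten randomized patients such a decision could look post hoc.

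**Working it through.** **The plan's own figures.** The SAP 7.6 inputs are 5 per arm, two-sided alpha 0.05, hazard ratio 0.1, and a control arm for which "The proportion of patients surviving (ie, event-free) in the control arm at Week 16 of the RW phase is 0.1".
- Control hazard = -ln(0.1)/16 = 0.1439 per week. TA 16-week event rate = 1 - 0.1^0.1 = 20.6%, as stated.
- The stated events are 4.9 + 1.8 = 6.7. Follow-up of 32 weeks per patient gives 5 × (1 - 0.1²) = 4.95 and 5 × (1 - 0.794²) = 1.85, or 6.8. With the 16-week RW maximum, the figures are 5 × 0.9 = 4.5 and 5 × 0.206 = 1.03, or 5.5. Hence about 5 to 7 events.
- Stated power: "These assumptions achieve 78.4% power based on a two-sided log rank test with an overall sample size of 10 patients". The Lakatos log-rank method gives 77.5% to 79.2% with 32 weeks per patient, which reproduces it, and about 68% to 72% with 16 weeks.

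**Constructed examples (assumptions, not forecasts).** There are five patients per arm, followed to RW week 16. At each event time with n at risk, n1 of them on TA, and d events:
- expected TA events E = d·n1/n
- variance V = d·(n1/n)·(1 - n1/n)·(n - d)/(n - 1)
- chi-square = (O - ΣE)²/ΣV on 1 df, where O is the observed number of TA events

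*Example A, placebo death.* Placebo reactivations occur at weeks 4, 8 and 8. One placebo patient dies at week 10, after a clear week-8 visit, and one stays event-free. TA has no events.
- Censored at week 8: ΣE = 5/10 + 2·5/9 = 1.611; ΣV = 0.250 + 0.432 = 0.682; chi-square = 1.611²/0.682 = 3.81; **p = 0.051**.
- Counted at week 10 (7 at risk, 5 on TA): ΣE = 1.611 + 0.714 = 2.325; ΣV = 0.682 + 0.204 = 0.886; chi-square = 6.10; **p = 0.0135**.

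*Example B, TA death.* Placebo reactivations occur at weeks 2, 4, 8 and 12, and one placebo patient stays event-free. One TA patient dies at week 6 after a clear week-4 visit, and there is no other TA event.
- Censored at week 4: O = 0; ΣE = 0.500 + 0.556 + 0.571 + 0.667 = 2.294; ΣV = 0.250 + 0.247 + 0.245 + 0.222 = 0.964; chi-square = 5.46; **p = 0.019**.
- Counted at week 6 (8 at risk, 5 on TA): O = 1; ΣE = 2.294 + 0.625 = 2.919; ΣV = 0.964 + 0.234 = 1.198; chi-square = (1 - 2.919)²/1.198 = 3.07; **p = 0.080**.

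Exact permutation p-values (all 252 allocations) cross 0.05 in the same directions: A, 0.167 censored and 0.048 counted; B, 0.048 censored and 0.127 counted.

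**Step 2 for the patient in Example B.** If failure means reactivation only (SAP 7.4.4.2), the split is 4/5 against 0/5 and Fisher's p = 2·5/210 = 0.048. If missing data make the patient a failure (7.4.5.2), the split is 4/5 against 1/5 and p = 2·(25 + 1)/252 = 0.206. With the death censored, step 1 passes at 0.019. Whether the sequence then passes step 2 depends on which SAP section is followed.

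**The case against.** The strongest reply is that the route is narrow. Unscheduled visits count for reactivation (SAP 6.4.1.1), dosing is every 2 days, and home care nurses report adverse events to the site physician (Protocol 17.1). Protocol 8.1 lists high fever, pancytopenia and hepatitis among the manifestations, and says untreated disease can progress to organ failure and death. Two new objective categories already make an event, so many disease-related deaths would follow a scored reactivation. After a reactivation, a later death does not matter for this endpoint. What remains is a sudden, unassessed or unrelated death, and it would be visible in the safety listing. This stands, and it lowers the priority. It does not supply the missing rule.

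Three stronger readings are tempting, and the documents do not support them.
- *The patient is credited as event-free to week 16.* No: only up to the last assessment without reactivation.
- *The rule favours the drug.* The direction depends on the arm of the death. In Example A it works against the drug.
- *A severe CNS relapse falls through the same gap, so CNS symptoms should be a primary event.* The enrolment definition does accept "Active clinical disease as evidenced by mAIDAI ≥ 4 or CNS manifestations", but exclusion criterion 6 bars the same list of manifestations at entry. Radiologic CNS involvement is already an objective category (Protocol Appendix 1, SAP Appendix A). No single category is an event by itself. Leaving out CNS symptoms is a stated choice to avoid bias (Protocol 10.5 and 12.2). A relapse seen only as CNS symptoms can be censored, but through the separate rule on rescue without objective reactivation (SAP 7.4.2.1). Promoting one symptom to a primary event would be a trade-off; it does not correct an error.

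**Conclusion.** The concern holds for death. Read as written, the plan censors a death without prior scored reactivation, gives that death no place in the primary estimand or its sensitivity analyses, and contradicts itself on whether the patient is a treatment failure. The censoring is probably informative, given the protocol's own account of the untreated disease.

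One such death is enough to move the log-rank p across 0.05 in either direction. This rests on constructed event times with five patients per arm; other configurations need not cross the threshold. The documents give no death rate, so the probability of such a case cannot be derived. Given the narrow route, this is an inexpensive improvement worth making before database lock. It does not show that the primary endpoint is unsound.

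**What to change.** - **SAP 6.4.1.1 and 7.4.2.1:** add death to the primary estimand with a composite strategy. The event is first reactivation or death from any cause in the RW phase, dated at death. State the time window and how this applies after rescue has started.
- **SAP 7.4.4.2 and 7.4.5.2:** count the same patients as treatment failures in step 2, and reconcile the missing-data rule with the reactivation-based definition.
- **SAP 7.4.2.3:** keep the current censoring rule as a sensitivity analysis. At most, add a supportive analysis that counts rescue without objective reactivation as an event.
- **SAP 7.7:** list the change, because Protocol 16.8 carries the present rule.

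The cost is a few sentences. Deaths and rescue use are already collected, so no new data are needed. The downside is that an unrelated death would count as an event in the primary analysis; the retained sensitivity analysis would show its effect.

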6.4.1.2 Secondary Efficacy Endpoints

The key secondary efficacy endpoint is

- Response to therapy (including complete response and partial response) in the SAOL phase from Week 10 onwards and observed at least at 2 consecutive visits at least 2 weeks apart during the SAOL phase

Other secondary efficacy endpoints include the following:

- Best response to therapy during the SAOL phase (including complete response and partial response and disease improvement)

- Duration of response to therapy (including complete response and partial response) during the SAOL phase
- Disease reactivation rate (ie, number of disease reactivations experienced per week while each subject is on the study treatment during the SAOL phase)
- Treatment failures (ie, patients who experience at least one disease reactivation), during the RW phase
- Intensity of disease reactivations (defined by the level of activity given by the mAIDAI – both objective and subjective criteria), during the RW phase and the SAOL phase
- Serum CRP during the RW phase and the SAOL phase
- Serum ferritin during the RW phase and the SAOL phase
- Improvement of fevers (if present at baseline) during the RW phase and the SAOL phase
- Improvement of hepato/splenomegaly (if present at baseline) during the RW phase and the SAOL phase
- Improvement in serum albumin and liver transaminases, anemia and/or platelet count (if present at baseline) during the RW phase and the SAOL phase
- Number of hospitalizations and hospital length of stay during the RW phase and the SAOL phase
- PGA during the RW phase and the SAOL phase
- Patient's or caregiver's qualitative evaluation of health status
- Presence of skin rash (evolution if present at baseline or appearance during the study) during the RW phase and the SAOL phase
- Tolerance to oral/enteral nutrition for hospitalized patients with intestinal dysfunction that was present at baseline during the RW phase and the SAOL phase
- Improvement of stool output for hospitalized patients if intestinal dysfunction was present at baseline during the RW phase and the SAOL phase

Active disease upon enrolment is defined as:

- Increased inflammatory markers, i.e., serum ferritin levels ≥ 500 ng/mL or serum CRP $\geq 2 \times$ ULN, and
- Active clinical disease as evidenced by mAIDAI ≥ 4 or CNS manifestations (i.e., seizures, altered mental status, signs of increased intracranial pressure, chronic papilledema, loss of vision, other sensorineural deficiencies, etc.)

For the definition of active disease upon enrolment, all mAIDAI components (subjective and objective) will be evaluated in line with previous protocol versions prior to version 6.0.

Response to Therapy is defined as:

1. In the 16-week RW phase, response to therapy (as primary endpoint of efficacy) will be assessed by prevention of disease reactivations during the 16-week treatment in the RW phase.
2. In the SAOL phase, response to therapy (as secondary endpoint of efficacy) will be assessed through the control of the active disease

For response to therapy, only the objective mAIDAI components will be evaluated as indicated below. Subjective mAIDAI components (see Appendix I of the clinical study protocol) will not be considered to avoid any bias in the efficacy assessment in the open label part of the study.

o **Complete response**

No major end organ damage (=objective mAIDAI components)

- No fever (body temperature $\leq 100.4^{\circ}\text{F}/38^{\circ}\text{C}$)
- No diarrhea
- No transaminitis and/or hepatomegaly
- No splenomegaly and/or adenopathy
- No rash
- No uveitis
- No arthritis
- No radiologic CNS involvement
- No cytopenia (HgB ≥ 9.0 and/or PLT ≥ 100 and/or WBC ≥ 3.0)

No systemic inflammation

- No hyperferritinemia (serum level $< 500 \text{ ng/mL}$)
- No increased CRP (serum level $< 2 \times \text{ULN}$)

Immunosuppressive therapies

- Discontinuation of systemic corticosteroids (excluding hydrocortisone for prevention of adrenal insufficiency) or other immunosuppressive therapies including biologics ongoing at baseline
- No start or dose increase of other immunosuppressive therapies including biologics

o **Partial response**

At least 50% reduction of the number of affected objective end organ damage categories at baseline and

- At least 50% of the systemic inflammatory markers (ferritin and/or CRP) increased at baseline reaching levels for complete response or
- Discontinuation of systemic corticosteroids (excluding hydrocortisone for prevention of adrenal insufficiency) or other immunosuppressive therapies including biologics ongoing at baseline

Partial response is thus a measure of the complete resolution of clinical manifestations in at least 50% of involved specific organ classes together with a reduction of the systemic inflammatory markers most relevant for this disease or the possibility to reduce other immunosuppressive therapies.

○ **Disease Improvement**

A third response category of Disease Improvement is introduced to be utilized as a description of best response and in order to better describe initial treatment response to therapy and disease evolution over time. This is only used for analysis purposes and will not be evaluated for the decision whether to be eligible for the start of the RW phase. Disease Improvement is defined as:

- Reduction of the number of affected objective end organ damage categories at baseline by at least 1 or
- Normalization (i.e., reaching levels for complete response) or improvement (> 50% change from baseline for laboratory markers but still exceeding levels for complete response) of at least 50% of the systemic inflammatory markers affected at baseline
- Systemic corticosteroids (excluding hydrocortisone for prevention of adrenal insufficiency) or other immunosuppressive therapies including biologics must be at the same or lower doses compared to baseline

